9.6 POST-TREATMENT ASSESSMENTS

Day 4, 5 and 7 Assessments

The following assessments will be done on Days 4, 5 and 7. Details about the below assessments are found in **Section 9.1**.

1. Vital Signs
2. EKG on day 7 and when available
3. Ventilator Parameters Assessment
4. Frontal Chest Radiograph on day 7 and when available
5. ABG; VBG if ABG is not available
6. SpO₂
7. Lung Injury Score (LIS)
8. Dead space fraction (Vd/Vt) on day 7
9. SOFA Score

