1.3 SCHEMA

TIME-EVENTS SCHEDULE

Measurement/Event	Baseline	Day 1	Day 2	Day 3	Day 4	Day 5	Day 7	Day 14	Day 28	Day 60	6M
Demographic/Admission Data/Medical Hx	X										
Etiology of ARDS	X										
Physical Exam	X										
Height/Body weight	X										
Time on ventilator prior to enrollment	X										
Pregnancy test	X										
Vital Signs (HR, SBP, DBP, MAP, T) ^B	X	X	X	X	X	X	X				
Central venous pressure ^B	A	A	A	A	A	A					
Electrocardiogram (EKG)	X	X	X	X	A	A	X				
Ventilator parameters ^{B, C}	X	X	X	X	X	X	X	X			
Chest X-ray (CXR) review ^D	X	A ^D	A ^D	A ^D	A ^D	A ^D	X				
Lung Injury Score (LIS)	X	X	X	X	X	X	X				
APACHE II Score	X										
SOFA Score ^E	X	X	X	X	X	X	X	X	X		
Glasgow Coma Score (GCS)	X	X	X	X	X	X	X	X	X ^F		
Richmond Agitation Sedation Scale (RASS)	X	X	X	X	X	X	X				
Arterial Blood Gas (ABG)	X										
ABG; Venous Blood Gas if ABG not available ^C		X	X	X	A	A	X	A			
SpO2	X	X	X	X	X	X	X	A			
ScvO2	A	A	A	A	A	A					
Complete blood count (CBC) ^C	X	X	X	X	A	A	A	A	A		
Basic metabolic panel ^C	X	A	A	A	A	A	A	A	A		
PT/PTT/INR ^C	A	A	A	A	A	A	A				
Serum CK, AST, ALT, Albumin, Total Protein ^C	A	A	A	A	A	A	A				
Bilirubin ^C	X	X	X	X	X	X	X	X	X		
Lactate ^C	X	X	X	X	A	A	A				
CO Administration Parameters / Treatment		X ^G	X ^G	X ^G							
Pulmonary Dead Space (Vd/Vt) Measurement		X	X	X			X				
COHb and SpCO		X ^G	X ^G	X ^G							
Vasopressors and inotropes ^B	X	X	X	X	X	X	X	X			
Fluid intake and output ^B	X	X	X	X	X	X					
Renal replacement therapy status	X	X	X	X	X	X	X	X			
Concomitant medications	X	X	X	X	X	X	X				
Adverse event monitoring ^H		X	X	X	X	X	X ^H				
Plasma isolation		X	X	X		X					

Measurement/Event	Baseline	Day 1	Day 2	Day 3	Day 4	Day 5	Day 7	Day 14	Day 28	Day 60	6M
RNA banking		X	X	X		X					
DNA banking – Cell pellet isolation		X	X	X		X					
Primary cell (PBMC) isolation		X				X					
Urine sample collection		X	X	X		X					
Discarded BAL and plasma ^I	A	A	A	A	A	A	A				
Microbiological results ^J	A	A	A	A	A	A	A	A	A		
Vital Status									X	X	X
Discharge Status									X	X	
Ventilator Status									X	X	
Vasopressor Status									X	X	
Neurocognitive Outcomes-MoCA-BLIND, Hayling											X

X - Required

A - When available

B - Data gathered at times indicated or until patient achieves 48 hours of unassisted breathing, whichever is sooner. Data will be obtained pre- and post-treatment on study drug administration days.

C - Measure during reference period (03:00-10:00), obtain at time closest to study drug administration if applicable

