4.3 PRIMARY SAFETY ENDPOINT

The primary safety endpoint is to evaluate the safety of inhaled CO, by determining COHb levels and the incidence of pre-specified administration-related adverse events.

- Safety of inhaled CO, defined by the incidence of pre-specified administration-related AEs (as defined below) and spontaneously reported AEs through study day 7.
 - Acute MI within 48 hours of study drug administration
 - Acute cerebrovascular accident (CVA) within 48 hours of study drug administration
 - New onset atrial or ventricular arrhythmia requiring DC cardioversion within 48 hours of study drug administration
 - Increased oxygenation requirements defined as: an increase in FiO_2 of ≥ 0.2 **AND** increase in $\text{PEEP} \geq 5$ cm H_2O within 6 hours of study drug administration
 - Increase in COHb $\geq 10\%$
 - Increase in lactate by ≥ 2 mmol/L within 6 hours of study drug administration

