7.1.4 CO MONITORING

The study drug concentration will be monitored continuously with the COventDS built-in analyzer to assure that the accurate dose is delivered. A physician investigator will assess subjects prior to daily iCO treatment. Subjects will have blood drawn daily for measurement of COHb and lactate prior to study drug administration. If COHb \geq 3% (assessed by unblinded physician) or lactate \geq 4 mmol/L, the study drug will be held and the subject will be reassessed for treatment the following day. An electrocardiogram (EKG) will also be performed daily prior to study drug administration to evaluate for cardiac exclusion criteria. Blood COHb levels will be measured with an IL GEM Premier Co-oximeter and SpCO measured with a noninvasive pulse oximeter (Masimo Radical-7).

Blood (arterial or venous) will also be drawn at 20, 60, 75, 90, and 180 minutes for safety monitoring of COHb levels. If an arterial line is not available, venous blood will be used for COHb monitoring as we⁴⁸ and others¹⁴³⁻¹⁴⁵ have shown that venous levels are as accurate and reliable as arterial measurements. Blood (arterial or venous) will also be drawn for blood gas analysis (using the local clinical lab) at 90 minutes or at the completion of treatment, if discontinued sooner than 90 minutes. If arterial blood is not available and venous blood gas is used, PaO₂/FiO₂ will be estimated using the formula $SpO_2/FiO_2 = 64 + 0.84 \times PaO_2/FiO_2$, as long as SpO₂ \leq 97% and subject remains intubated as described in the Statistical Analysis Plan.

The unblinded physician will review and adjudicate COHb measurements and communicate any study drug treatment holds to the administering study staff. COHb levels will be entered into the electronic case report forms (eCRFs) in a separate limited-access project in StudyTRAX by the unblinded RT or physician. The study drug will be administered for up to 90 minutes daily for up to 3 days following randomization or until discontinuation of mechanical ventilation, whichever occurs first.

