9.5 STUDY DRUG ADMINISTRATION ASSESSMENTS (DAY 1-3)

The following assessments will be done on Days 1 – 3 prior to study drug administration. **No treatment will be started before these assessments are performed and the pre-treatment checklist is completed by the study investigator**

Calibration of IL GEM Premier Co-oximeter and COventDS: Calibration will be performed according to device manuals and SOP. Documentation of calibration will be kept in study files.

COHb Level: The baseline COHb level will be drawn and assessed by an unblinded physician investigator, just prior (less than 15 minutes) to starting the study drug administration. COHb will be measured by study investigators using an IL GEM Premier Co-oximeter at the patient's bedside. These results are obtained within less than 5 minutes. The study drug will not be started until this result is obtained and reviewed for a potential study hold. All COHb level result printouts should be filed in the unblinded subject file.

Lactate Level: Lactate level will be measured and assessed daily by the local laboratory at each center prior to study drug administration. The study drug will not be started until this result is obtained and reviewed by the study physician investigator for a potential study hold.

Hemoglobin Level: Hemoglobin will be measured and assessed daily prior to study drug administration. The hemoglobin level will be measured by the local laboratory at each center. The study drug will not be started until this result is obtained and reviewed by the study physician investigator for a potential study hold.

EKG: A 12 lead EKG will be obtained and reviewed daily by the study staff physician prior to study drug administration to evaluate for cardiac exclusion criteria ie. acute MI, ACS, or unstable atrial or ventricular arrhythmia. The study drug will not be started until the EKG is obtained and reviewed by the study physician investigator for a potential study hold. The EKG will also be officially read locally at each site.

Review Ventilator Parameters: The study staff will record ventilator parameters prior to starting study drug administration.

Calculate Deadspace (Vd/Vt): Dead space fraction will be measured daily by the administering RT or physician prior to study drug administration using a NICO or NM3 monitor (Respironics) and the PCO₂ obtained from an arterial or venous blood gas.

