9.5.2 STUDY DRUG ADMINISTRATION AND MONITORING

The study drug will be administered for up to 90 minutes daily for up to 3 days following randomization or until discontinuation of mechanical ventilation, whichever occurs first according to **Section 7.1.9**. See **Sections 7.1.6, 7.1.7, and 7.1.8** for information about study drug hold, interruption, and permanent discontinuation criteria.

Monitoring during Study Drug Administration:

Subjects will be monitored with continuous pulse oximetry, cardiac monitoring, and either intermittent (at least every 15 minutes) or continuous blood pressure monitoring (if an arterial line is in place) throughout the course of the 90 minute study drug treatment.

SpCO and SpO₂ will be monitored continuously using a Masimo Rad-7 non-invasive pulse oximeter, and recorded at the time points specified below. COHb levels will be measured using an IL GEM Premier Co-oximeter and recorded at the time points specified below. Arterial or venous blood will be drawn for blood gas analysis prior to treatment and at the completion of study drug administration (90 min or earlier if discontinued prior to 90 min). If study drug treatment is discontinued prior to 90 min, all of the scheduled 90-minute measurements will be made and recorded at the time of study drug discontinuation.

Ambient CO levels will be monitored continuously using a Dräger Pac 7000 CO detector, and recorded at the time points specified below.

	ABG or VBG (pH, PCO ₂ , PO ₂)	FiO ₂	COHb level (IL GEM Premier co-oximeter)	CFK look-up table (Appendix B or StudyTRAX)	SpCO (Masimo Rad-7)	SpO ₂ (Masimo Rad-7)	Ambient CO Level (Dräger Pac CO detector)
Pre-treatment	X	X	X		X	X	X
20 min			X	X	X	X	X
60 min			X		X	X	X
75 min			X		X	X	X
90 min*	X	X	X		X	X	X
180 min			X		X	X	X

*90 min or upon completion of study product if discontinued sooner than 90 min.

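### The primary safety endpoint counts acute MI within 48 hours of dosing, but no protocol-required EKG falls within 48 hours of a Day 3 dose

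*Combined protocol and SAP*

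**What the plan says.** Section 4.3 lists "Acute MI within 48 hours of study drug administration" among the pre-specified administration-related events in the primary safety endpoint. Section 10.1 repeats it, section 7.1.8 makes it a reason for permanent discontinuation, and section 9.7.4 lists it among the events that count by definition as suspected adverse reactions.

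The EKG row of the Time-Events Schedule (section 1.3) shows X (required) at Baseline and on Days 1, 2, 3 and 7. Days 4 and 5 carry the code "A - When available". Section 9.6 says the same for the post-treatment days: "EKG on day 7 and when available".

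The Day 1 to 3 tracings are pre-dose. Section 9.5 states: "A 12 lead EKG will be obtained and reviewed daily by the study staff physician prior to study drug administration". Section 7.1.4 gives the purpose: "An electrocardiogram (EKG) will also be performed daily prior to study drug administration to evaluate for cardiac exclusion criteria".

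Dosing is confined to the same three days: "The study drug will be administered for up to 90 minutes daily for up to 3 days following randomization" (section 9.5.2). Footnote B of the schedule, "Data will be obtained pre- and post-treatment on study drug administration days", is attached to vital signs, ventilator parameters and some other rows, but not to the EKG row.

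**The concern.** A safety component with a 48-hour window needs some planned observation inside that window after each dose. Here the EKGs appear to be placed as hold checks before dosing. They cover the windows after doses 1 and 2 only because the next day's pre-dose tracing happens to fall inside them. After a Day 3 dose there is no next pre-dose tracing.

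No other scheduled test fills the gap. Troponin is not in the Time-Events Schedule, and CK is recorded only when available. The monitoring table in 9.5.2 contains no EKG, and continuous cardiac monitoring is specified only for the 90-minute administration. Section 6.5 expects most subjects to have impaired decision-making from critical illness or sedation, so reported symptoms are a weak trigger for a clinical EKG.

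At stake is how a report of no MI, or few MIs, within 48 hours of administration should be read. After the last planned dose, ascertainment depends on local practice. An infarct first visible on the Day 7 EKG could not be dated to the window from that tracing.

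**Working it through.** The plan gives no figure to reproduce here. The check is one of timing.

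**Inputs**
- Window: 48 hours from dosing (4.3, 10.1).
- Dosing days: 1, 2 and 3 (Time-Events Schedule, 9.5.2).
- Required EKG days after the first dose: 2, 3 and 7 (Time-Events Schedule, 9.6). Those on Days 2 and 3 precede that day's dose (7.1.4, 9.5).
- Study days are calendar days (1.4).

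**Formula.** For a dose on Day d and an EKG on Day e, the nominal gap is 24(e − d) hours. Because only the calendar day is fixed, the gap can range from 24(e − d − 1) to 24(e − d + 1) hours.

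| Dose day | EKG day | Nominal gap (h) | Range (h) | Inside 48 h? |
|---|---|---|---|---|
| 1 | 2 | 24 | 0–48 | Yes |
| 1 | 3 | 48 | 24–72 | Depends on clock times |
| 1 | 7 | 144 | 120–168 | No |
| 2 | 3 | 24 | 0–48 | Yes |
| 2 | 7 | 120 | 96–144 | No |
| 3 | 7 | 96 | 72–120 | No |

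The shortest possible gap from a Day 3 dose to the Day 7 EKG is 24 × (7 − 3 − 1) = 72 hours, which exceeds 48. The number of required EKGs in the 48 hours after a Day 3 dose is therefore 0, whatever the clock times.

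**Extent.** A fully dosed subject has 3 dose windows, of which 1 has no required EKG. If all 32 subjects receive three doses, that is 32 × 1 = 32 of 32 × 3 = 96 windows, with 16 of 48 in each arm. This is a ceiling. A subject whose last dose is on Day 1 or Day 2 still has EKGs marked as required through Day 3, so at least one normally falls inside that subject's last window.

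**A Day 4 EKG.** The nominal gap from a Day 3 dose is 24 × (4 − 3) = 24 hours, with a range of 24 × 0 = 0 to 24 × 2 = 48 hours. It falls inside the window for any clock times. It would put the Day 3 dose on the same footing as the Day 2 dose now has.

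**The case against.** The strongest reply is that the endpoint component is acute MI, not MI detected by a scheduled EKG. Section 9.7.4 has blinded physicians determine adverse events daily through Day 7, evaluate changes in laboratory values and physical signs, and record time of onset. Vital signs are required on Days 4 and 5, and clinical EKGs are recorded when available. This stands. A reader might infer that an MI after the third dose is found only if a clinician happens to order an EKG, or that an MI noticed late can never be dated. The documents do not support either reading. What remains is that the daily review names no test, so on Days 4 and 5 it draws on whatever was done locally.

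Three other stronger readings are tempting but unsupported:
- **Bias between arms.** The schedule is identical in both arms. The documents show a route to under-counting, not a differential one.
- **Greater risk after dose 3.** Section 5.3 says that CO will not accumulate, because treatments are separated by 4 to 6 elimination half-lives. Dose 3 matters here only because its window has no required tracing.
- **A Day 7 EKG without endpoint value.** The primary safety endpoint also includes spontaneously reported adverse events through Day 7, and Day 7 ends the capture period. Its EKG is the only required post-treatment tracing, so dropping it has a cost.

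The absence of scheduled troponin should not be pressed far. Section 7.1.6 notes that troponin may be raised in sepsis and ARDS without MI.

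Finally, a single Day 4 tracing does not cover the whole 48 hours. That is true, but it also applies to the Day 3 tracing that now follows a Day 2 dose.

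**Conclusion.** The point holds for subjects dosed on Day 3. The schedule requires no EKG within 48 hours of that dose, although MI in that window is part of the primary safety endpoint. The consequence is possible under-counting of MI after the last dose in both arms, since ascertainment there rests on daily adverse-event review and clinically ordered tracings. The size is at most 1 of 3 dose windows per fully dosed subject, with a ceiling of 32 of 96. How many MIs would be missed cannot be estimated from the documents.

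This assumes doses on Days 1 to 3 as scheduled and calendar study days. It concerns required EKGs only. It is a modest weakness that is cheap to repair, and it should be repaired.

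**What to change.** Reconcile the EKG schedule with the 48-hour window. In the Time-Events Schedule and section 9.6, make the Day 4 EKG required and change Day 7 to when-available. State that the Day 4 tracing is read against the pre-dose Day 3 tracing for the MI component.

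Required EKGs per subject stay at five: Baseline and Days 1, 2, 3 and 7 now; Baseline and Days 1, 2, 3 and 4 after the change. The cost is a short schedule amendment and the loss of the only required tracing at the end of the Day 7 adverse-event period. If the sponsor wants to keep Day 7, requiring both adds one EKG per subject, or 32 in all if every subject has it.

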10. GCS
11. RASS
12. CBC if available and requested by treating physician
13. Basic metabolic panel if available and requested by treating physician
14. PT/PTT/INR if available and requested by treating physician
15. Serum CK, AST, ALT, Albumin, Total Protein if available and requested by treating physician
16. Bilirubin
17. Lactate if available
18. Vasopressors and Inotropes Review
19. Fluid intake, fluid output (most recent 24 hour value) or mean hourly value for most recently available period
20. Renal replacement therapy status
21. Concomitant Medications Review
22. Adverse Event Monitoring
23. Blood for Biomarker Collection
24. Urine Sample Collection
25. Microbiological results when available
26. Discarded BAL fluid and plasma if available

Day 14 Assessments

The following assessments will be done on Day 14. Details about the below assessments are found in **Section 9.1**.

1. Ventilator Parameters Assessment
2. SOFA Score
3. GCS
4. Total Bilirubin
5. Vasopressors and Inotropes Review
6. Renal Replacement Therapy Status
7. Microbiological results when available

Day 28 Assessments

The following assessments will be done on Day 28. Details about the below assessments are found in **Section 9.1**.

1. SOFA Score
2. GCS
3. Bilirubin
4. Microbiological results when available
5. Vital Status
6. Discharge, Ventilator, and Vasopressor Status

Day 60 Assessments

The following assessments will be done on Day 60. Details about the below assessments are found in **Section 9.1**.

1. Vital Status
2. Discharge, Ventilator, and Vasopressor Status

6 Month Follow-up Assessments

The following assessments will be done at 6 months. Details about the below assessments are found in **Section 9.1**.

1. Vital Status
2. Neurocognitive Testing – Montreal Cognitive Assessment (MoCA)-BLIND, Hayling sentence completion test

9.6.1 ASSESSMENTS AFTER HOSPITALIZATION

Vital status will be collected at 28 days, 60 days, and 6 months through telephone interviews with participants. Surrogates will be contacted in the case that subjects cannot be reached. The site investigator or designee will make every effort to contact the participant or surrogate (where possible, 3 telephone calls and, if necessary, a certified letter to the participant's last known mailing address or local equivalent methods). These contact attempts should be documented in the participant's medical record or study file.

In addition, we will verify duration of survival for participants lost to follow-up or noted to have died using the Centers for Disease Control and Prevention's National Death Index (National Death Index, 2000). We will use each subject's SSN for an exact NDI match. We will collect contact information for the subject and alternative contact information on up to 3 individuals. This information and the SSN will be collected on paper at the time of consent. Contact information and SSN will be maintained on paper and will not appear in the DCC database. In addition to vital status, long term cognitive function will also be assessed at 6 months. Cognitive impairment is highly prevalent among survivors of critical illness¹⁵²⁻¹⁵⁷. In addition, neurocognitive deficits observed at 3 months after hospitalization persist at 12 months following critical illness in the majority of patients¹⁵⁷. In survivors of ARDS, cognitive impairment has been observed in approximately 30-55% of patients following one year of hospitalization^{152,156}. Similarly, moderate to severe cognitive impairment has been observed in survivors of severe sepsis up to one year following hospitalization¹⁵³.

Several studies have demonstrated the safety of CO, including lack of adverse neurocognitive effects, at levels of COHb < 10%, which exceed the levels anticipated in our study. Neurocognitive effects of CO have been extensively evaluated in previous human studies^{116,158}, our endotoxin study in healthy volunteers (NCT00094406), and our recent trial of CO treatment in IPF patients (NCT01214187)¹²⁰. Stewart et al.

demonstrated no impairment in performance testing in healthy humans exposed to CO at 100 ppm for 8 hours with COHb levels of 11-13%¹¹⁶. In addition, we demonstrated lack of adverse neurocognitive effects in healthy volunteers exposed to CO at 100 ppm for 6 hours with COHb 6.5% ± 1.7%. In addition, a recent study by Linde Gas Therapeutics assessed the safety of inhaled CO in 32 healthy subjects. CO was well tolerated with no significant neurocognitive effects observed in subjects with COHb levels of 2-8.8%. In our CO IPF trial, neurocognitive function was evaluated using the Montreal Cognitive Assessment (MoCA) tool. Subjects with IPF receiving biweekly treatment with inhaled CO at 100-200 ppm for 2 hours demonstrated no impairment in neurocognitive function after 2.5 weeks of follow-up. In addition to these studies, a recent review of the literature suggests that neurocognitive effects are only seen once COHb rises above 15-20%¹⁵⁸.

In this study, we will use a telephone version of the MoCA^{159,160}, which consists of 4 items examining attention, verbal learning and memory, executive functions/language, and orientation and can be administered in 5 minutes. The MoCA has been shown to be a valid and feasible screening tool to assess cognitive function in patients following CVA and acute coronary syndrome¹⁵⁹⁻¹⁶³. We will also use a telephone version of the Hayling sentence completion test to further evaluate executive function^{164,165} which is commonly impaired in ARDS survivors¹⁵²⁻¹⁵⁷.

9.7 ADVERSE EVENTS AND SERIOUS ADVERSE EVENTS

9.7.1 DEFINITION OF ADVERSE EVENTS (AE)

Adverse event means any untoward medical occurrence associated with the use of an intervention in humans, whether or not considered intervention-related (21 CFR 312.32 (a)).

9.7.2 DEFINITION OF SERIOUS ADVERSE EVENTS (SAE)

An adverse event (AE) or suspected adverse reaction is considered "serious" if, in the view of either the investigator or sponsor, it results in any of the following outcomes:

- results in death;
- is life threatening (places the subject at immediate risk of death from the event as it occurred);
- requires inpatient hospitalization or prolongation of existing hospitalization;
- results in a persistent or significant disability/incapacity;
- results in a congenital anomaly/birth defect; or
- any other adverse event that, based upon appropriate medical judgment, may jeopardize the subject's health and may require medical or surgical intervention to prevent one of the outcomes listed above.

Organ failures related to ARDS or the patient's underlying condition that are systematically captured by the protocol should not be reported as adverse events ***unless they are considered to be study related.***

If the suspected adverse reaction is unexpected, it will be classified as a serious unexpected suspected adverse reaction (SUSAR).

